8.7.5 Adverse Events of Special Interest

Not applicable.

8.7.6 Procedure for Breaking the Blind

This trial does not use blinding procedures.

8.7.7 Follow-up of Adverse Events

8.7.7.1 Follow-up of Nonserious Adverse Events

Nonserious AEs that are identified at any time during the trial must be recorded on the AE eCRF with the current status (ongoing or resolved/recovered) noted. All nonserious events (that are not IREs) that are ongoing at the last scheduled contact will be recorded as ongoing in the eCRF. For any AE having been identified throughout the trial, or during analysis, additional relevant medical history information may be requested by the sponsor to further ascertain causality (including, but not limited to, information such as risk-related behavior, family history, and occupation).

8.7.7.2 Follow-up of Immediately Reportable Events and Serious Adverse Events

This trial requires that subjects be actively monitored for IREs (SAEs) up to 7 days (+2 days) after applying the D-Tect Patch and DOIs.

Immediately reportable events that are **identified or ongoing at the last scheduled contact** must be recorded as such on the AE eCRF page and the IRE form. If updated information (eg, resolved status) on IRE status becomes available after a subject's last scheduled contact (up to the last in-clinic visit for the entire trial), this must be reported to the sponsor and recorded on the AE eCRF page and the IRE form, according to the appropriate reporting procedures described in Section 8.7.3.

Confidential - Proprietary Information

37

It is expected that the investigator will provide or arrange appropriate supportive care for the subject and will provide prompt updates on the subject's status to the sponsor. The investigator will follow the IREs until:

- the events are resolved,
- the events have stabilized,
- the subject is lost to follow-up, or
- the subject has died. •

Resolution means that the subject has returned to the baseline state of health and stabilized means that the investigator does not expect any further improvement or worsening of the subject's condition. The investigator will continue to report any significant follow-up information to the sponsor up to the point the event has resolved or stabilized, or the subject is lost to follow-up, or has died.

8.7.7.3 Follow-up and Reporting of Immediately Reportable Events **Occurring After Last Scheduled Contact**

Any new IREs (SAEs) reported to the investigator which occur after the last scheduled contact and are determined by the investigator to be reasonably associated with the use of the trial intervention(s), should be reported to the sponsor according to the procedures outlined in Section 8.7.3. This may include IREs that are captured on follow-up telephone contact or at any other time point after the defined trial period. Any significant follow-up information should continue to be reported to the sponsor until the events are resolved or stabilized, or the subject is lost to follow-up or has died.

8.8 Treatment of Overdose

For this trial, any dose of Abilify MyCite that is greater than the planned dose level (ie, subjects are planned to ingest Abilify MyCite at the same dose as their currently prescribed aripiprazole) will be considered an overdose for Cohort 2. In the event of an overdose, refer to the Abilify MyCite USPI for management of overdosage. To mitigate the risk of potential overdose, site staff will confirm that subjects do not take their prescribed dose of aripiprazole at home prior to the DOI of Abilify MyCite.

8.9 Subject Assessment Recording

Not applicable.

Confidential - Proprietary Information

38

8.10 Other Assessments

8.10.1 Positive Detection Accuracy

The number of total DOIs will be reported by the site on the eCRF. Positive detections will be downloaded from the trial mobile device(s) for analysis.

8.10.2 Detection Latency Measures

The DOI time will be recorded in the eCRF to the nearest minute by the site. Signal detection times will be downloaded from the trial mobile device(s) for analysis.

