The IEM is a tiny device that is composed of a 1 mm x 1 mm x 0.3 mm silicon integrated circuit coated with thin layers of minerals and metals that rests in the center of an edible, cellulose-based disc. Within a few minutes after ingestion, the sensor uses the fluid in the stomach (pH independent) to provide the electrolyte for a biogalvanic battery formed by thin layers of the essential dietary minerals, magnesium, and copper deposited on the sensor's surface. The ensuing current is modulated by the IEMs microprocessor and creates an electric field that propagates through the body tissues to the skin surface. The modulated current is detected, decoded, recorded, and date- and time-stamped by the patch, which acts as a receiver. The IEM communicates with its identifier for a finite period of time of a few minutes and can be detected by the patch only when the patch is adherent to the subject's skin, thus providing personal privacy for data recording. This mimics the process whereby bioelectric signals from cardiomyocytes reach the electrodes of an electrocardiograph on the surface of the body. Each sensor's identifier is unique which makes it possible to differentiate multiple IEMs from one another when they are ingested at the same time. The IEM becomes inactive subsequently and is excreted in the feces. The IEM consists of tiny amounts of naturally occurring minerals found in the body and in food.

For this trial, testing will involve directly observed ingestions (DOIs) of the IEMs. Research staff will administer the IEMs to subjects and observe and record the time of each individual ingestion event.

16

- For Cohort 1: The miniature IEM tablet (MIT) dose form will be used for testing. There are no active pharmaceutical ingredients in this dose form. Subjects will take 15 MITs over the course of 1 day, with approximately 15 (-5 / +15) minutes between ingestions.
- For Cohort 2: A single dose of Abilify MyCite (aripiprazole embedded with an IEM) will be used for testing. Abilify MyCite will be dispensed to subjects at the same dose as their current aripiprazole prescription. Abilify MyCite will be ingested at one time point during the trial.

Mobile Device with Mobile Application

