9.1 Endpoints

| Objectives | Endpoints |
|---|---|
| Primary | Primary endpoint for PDA |
| • Evaluate PDA and detection latency measures for the D-Tect Patch. | • Estimate PDA with the CI lower limit greater than 95% when a subject is wearing the D-Tect Patch. |
| | Primary endpoint for Detection Latency |
| | • The mean and median for three latency measures: Patch Detection Latency, Ingestion Data Transfer Latency, and Total Detection Latency (See Section 10.7 for detailed definition). |
| Secondary | Safety |
| • To collect and characterize AEs associated with the device. | • The frequency and severity of AEs, device- related AEs, serious AEs (SAEs), and AEs leading to discontinuation |

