10.7 Definition of Detection Latency

As shown in the system diagram in Figure 1, there are 4 time-stamped events (TSEs) associated with measuring detection latency shown in Table 3.

Table 3: Time-stamped events (TSEs) associated with measuring detection latency

| TSE 1 | Subject takes tablet. Directly observed ingestion time is recorded by the clinician. |
|-------|--|
| TSE 2 | Tablet sends signal to the patch. Tablet is detected & recorded by the patch as an IEM record with a timestamp. |
| TSE 3 | Patch sends ingestion data to phone. The tablet ingestion data is communicated to and recorded by the mobile device as a pill-ingestion-metric with a timestamp. |
| TSE 4 | Tablet ingestion data is displayed. The tablet display event is triggered on the mobile device as a pill-display-event with a timestamp. |

Figure 1: Digital Medicine System

The latency measurements between each of above timestamps are defined in Table 4.

Table 4. Latency measurements

| Table 4. Datency m | casul cilicitis | |
|--------------------|-----------------|---------------|
| CCI | | Page 11 of 20 |
| | | Page 11 of 20 |

Strictly Confidential. © 2023, PRA Health Sciences. All rights reserved.

Statistical Analysis Plan (SAP) Version Date: 22-JUN-2023 Sponsor: Otsuka Pharmaceutical Development & Commercialization, Inc. Protocol No: 031-201-00521

| Latency Measurements | Definition | Maximum Observation Time |
|---------------------------------|---|-----------------------------|
| Patch Detection Latency | Time between TSE 1 and TSE 2 in seconds | 10 minutes/600 seconds |
| Ingestion Data Transfer Latency | Time between TSE 2 and TSE 4 in seconds | 5 minutes/300 seconds |
| Total Detection Latency | Time between TSE 1 and TSE 4 in seconds | 15 minutes/900 seconds |

For Kaplan-Meier estimate, if the DOI is successfully detected, it will be treated as positive detection and event = "1"; If the DOI is not successfully detected or latencies have been larger than the maximum observation time (defined above in Table 4), the data will be considered as censored data and event = "0", where time to event is defined as maximum observation time.

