12.5.2 Detection Latency Measures

As defined in **Table 3**, the directly observed ingestion time (TSE 1) is recorded in the CRF. Other signal detection times (TSE 2-4) will be downloaded from the trial mobile device(s) for analysis. The derivation of detection latency measures, including Patch Detection Latency, Ingestion Data Transfer Latency, and Total Detection Latency, are provided in **Table 4**.

The three detection latency measures for all DOIs will be summarized using descriptive statistics, for **FAS-Cohort 1** and **FAS-Cohort 2** separately.

Furthermore, two Kaplan-Meier curves will be plotted for all of the latency times (all DOIs), for **FAS-Cohort 1** and **FAS-Cohort 2** separately. The three detection latency measures will be displayed as three curves on the plot. A table will be provided to show the summary of survival status, the median (50% survival time), and 25% and 75% percentiles of survival by Kaplan-Meier estimate.

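### Ingestion time is recorded only to the nearest minute, while two of the three primary latencies are computed from it in seconds: up to 30 s of rounding error per ingestion and no rule for negative values (minor)

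*Protocol*

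**What the plan says.** On the start time, Protocol 8.10.2 states: "The DOI time will be recorded in the eCRF to the nearest minute by the site". SAP 12.5.2 uses the same field: "the directly observed ingestion time (TSE 1) is recorded in the CRF". The later time-stamped events (TSEs) come from elsewhere: "Other signal detection times (TSE 2-4) will be downloaded from the trial mobile device(s) for analysis".

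SAP 10.7, Table 4, then defines the three latencies:

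- Patch Detection Latency: "Time between TSE 1 and TSE 2 in seconds"
- Ingestion Data Transfer Latency: "Time between TSE 2 and TSE 4 in seconds"
- Total Detection Latency: "Time between TSE 1 and TSE 4 in seconds"

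All three are primary. Protocol Table 3-1 names the medians, and SAP 9.1 names "The mean and median for three latency measures: Patch Detection Latency, Ingestion Data Transfer Latency, and Total Detection Latency". SAP 12.0 reports mean and median to one decimal place more than the raw data.

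Table 4 sets maximum observation times of 600, 300 and 900 s. It sets no minimum. SAP 10.8 analyses values as observed. On how long detection should take, the documents offer only a qualitative remark in Protocol Section 2, under Ingestible Event Marker: "Within a few minutes after ingestion, the sensor uses the fluid in the stomach".

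**The concern.** Patch and Total Detection Latency subtract a start time known to the minute from an end time stamped by a device, and the result is reported in seconds. If the true latency is a minute or two, the recording unit is of the same order as the quantity measured. Transfer latency does not use the ingestion time and is unaffected.

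Two things are at stake. First, the variability, extremes and quartiles of two primary measures include recording error that the SAP neither removes nor mentions. Second, a short latency can come out below zero. For example, a tablet swallowed at 10:00:40 is recorded as 10:01; if it is detected at 10:00:50, the true 10 s becomes -10 s. The SAP does not say how such a value enters the descriptive summaries or the Kaplan-Meier estimate, so someone would have to decide after seeing the data.

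**Working it through.** The plan states no figure for latency precision, so there is nothing to reproduce. The check works from the recording rule.

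**Inputs from the documents.** Recording unit 60 s (Protocol 8.10.2); 24 x 15 = 360 ingestions in Cohort 1 and 30 in Cohort 2 (Protocol 9.1); upper limits as in SAP Table 4.

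**Assumptions.** Ingestions fall uniformly within the minute, and the rounding error is independent of the latency. Latency is log-normal with median 20 to 180 s and log-SD 0.5 or 0.8. The latency distribution is assumed because the documents give none.

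**Step 1: error per ingestion.** Rounding to 60 s gives an error between -30 and +30 s. SD = 60/√12 = 17.3 s. The expected error is 0, so the mean is not shifted.

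**Step 2: chance of a negative value.** For true latency L under 30 s, P(negative) = (30 - L)/60. At L = 0, 10 and 20 s this is 50%, 33% and 17%. At 30 s or more it is 0.

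**Step 3: effect on the summaries** (1,000,000 draws per row for the observed median and negative share; 4,000 simulated samples for each standard error). SE columns show exact time → rounded time.

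| True median (s) | Log-SD | Observed median (s) | Negative | SE of median, n = 30 (s) | SE of median, n = 360 (s) |
|---|---|---|---|---|---|
| 20 | 0.5 | 22.4 | 16.1% | 2.2 → 5.3 | 0.66 → 1.64 |
| 20 | 0.8 | 24.3 | 17.0% | 3.6 → 5.8 | 1.05 → 1.76 |
| 30 | 0.5 | 32.8 | 7.5% | 3.4 → 5.7 | 0.99 → 1.68 |
| 30 | 0.8 | 34.1 | 10.5% | 5.5 → 6.6 | 1.58 → 1.91 |
| 60 | 0.5 | 62.2 | 0.8% | 6.7 → 7.7 | 1.97 → 2.22 |
| 60 | 0.8 | 62.5 | 3.1% | 11.0 → 11.2 | 3.15 → 3.26 |
| 120 | 0.5 | 121.3 | 0.02% | 13.6 → 14.0 | 4.01 → 4.10 |
| 120 | 0.8 | 121.2 | 0.5% | 21.7 → 21.8 | 6.32 → 6.36 |
| 180 | 0.5 | 180.8 | 0.0% | 19.8 → 20.3 | 5.94 → 6.09 |
| 180 | 0.8 | 180.7 | 0.1% | 33.2 → 33.2 | 9.47 → 9.51 |

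The simulated means agree with the true means to within 0.1 s. At most 0.4% of values change sides of the 600 s limit for Patch Detection Latency.

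**Step 4: spread.** Observed SD = √(true SD² + 17.3²). For a log-normal with log-SD 0.5, true SD = mean x √(e^0.25 - 1) = mean x 0.533.

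- Median 30 s: mean 34.0, SD 18.1 becomes √(18.1² + 17.3²) = 25.0 s.
- Median 120 s: mean 136.0, SD 72.5 becomes √(72.5² + 17.3²) = 74.5 s. The quartiles move only from 86 and 168 s to 85 and 170 s.

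**Step 5: a departure from the plan, shown separately.** If staff copied the displayed minute instead of rounding, the error would run from 0 to 60 s with mean 30 s. No negatives would arise. The simulated medians would rise by about 31 to 34 s (30 becomes 63 to 64, 60 becomes 92 to 93, 120 becomes 151).

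**The case against.** The strongest reply is that under the plan as written the primary summaries barely move. The protocol's endpoint is the median, which shifts by about 4 s or less. The mean, added by the SAP, is essentially unbiased. The SAP calls the study exploratory (8.1 and 9.0), and latency has no threshold, margin or test. Even in Cohort 2, rounding contributes only 17.3/√30 = 3.2 s to the standard error of the mean, and with one ingestion per subject these errors are independent across subjects. All of this stands, and it keeps the point minor.

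Three stronger readings are tempting but not supported:

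- *The primary medians are biased by about 30 s.* That requires staff to truncate. Protocol 8.10.2 says to round. Truncation is a risk of conduct, and it cannot occur in the same record as a rounding negative.
- *Negative values will be common, or will break the Kaplan-Meier estimate.* A negative needs a true latency under 30 s, and the documents do not say how often that occurs. Their remark about a few minutes sets no lower bound but does not suggest medians of 20 or 30 s. The product-limit estimator works on ordering, and the documents do not state how the software would treat a negative time.
- *The staff and device clocks are not synchronised.* Neither document mentions synchronisation, but the operations manual (Protocol 6.2) and the CRF (SAP 6.0) may do so and were not available.

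The reply leaves two facts untouched: the time field is coarser than the unit of analysis, and the SAP has no rule below zero.

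**Conclusion.** The point holds as a minor one. Two of three primary latencies carry a per-ingestion rounding error of up to ±30 s. The 30 s bound and the absence of a rule for negatives follow from the text alone. The SD also needs ingestions to be spread evenly within the minute; if staff tend to dose on the minute, the error is smaller. Every statement about medians, standard errors and negative shares rests on the assumed log-normal latencies.

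Within that range the practical loss depends on the true latency. At a median of two minutes or more it is hardly visible. At about a minute or less it shows in the spread, minimum, percentiles and, for n = 30, the precision of the median.

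A reader might infer from Protocol 4.2, which aims to show performance comparable to predecessor patches, that a half-minute shift undermines that comparison. The documents do not support this: such a shift is not a consequence of the plan, and neither document specifies a latency comparison, reference value or margin.

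**What to change.** 1. Change Protocol 8.10.2 and the DOI field in the eCRF to HH:MM:SS, read from the paired mobile device or from a clock set to it. Rounding error then falls to at most 0.5 s (SD 1/√12 = 0.29 s), and copying a displayed minute is no longer possible.
2. This aligns TSE 1 with the phone's clock only. TSE 2 is stamped by the patch (Protocol Section 2), so any offset between patch and phone remains and should be checked.
3. Add to SAP 10.7 a prespecified rule for any negative latency, for example set it to 0 s and report the count. State whether the rule covers the descriptive summaries as well as the Kaplan-Meier estimate: it corrects only one direction of error, so it would raise the mean slightly.
4. If the eCRF cannot be changed, keep the analysis in seconds and state the ±30 s limit with the results. Do not report whole minutes. That discards valid device seconds and can make the median worse: in the 30 s rows above, the observed median of 33 to 34 s would round to 60 s.

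Cost: one changed time field and one line of site instruction for staff who already observe and record each ingestion. Accuracy will still be limited by how exactly staff can see the moment of swallowing, so second-level recording should not be presented as second-level accuracy.

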8.10.3 Sleep Diary

On Day 1 of the trial, subjects will be sent home with a sleep diary to complete each day until they return for the follow-up visit on Day 8 [+ 2 days]. Instructions on how to complete the sleep diary will be provided to the subject by the trial staff. The sleep diary responses will be reported by the site on the eCRF.

9 Statistical Considerations

9.1 Sample Size

For Cohort 1, a minimum of 24 subjects are planned to complete 15 DOIs per subject. With this assumption, 24 subjects with 360 ingestions will provide sufficient power to ensure the lower bound of the 95% confidence interval (CI) for PDA is at 95% assuming the PDA rate of 97.3% of the D-Tect Patch using binomial distribution.

For Cohort 2, there is no formal sample size calculation. A minimum of 30 subjects are planned to complete a single DOI of Abilify MyCite.

9.2 Datasets for Analysis

The following analysis samples are defined for this trial:

- Enrolled Sample: all subjects who sign an ICF and enter the trial (and only subjects who meet all the inclusion criteria and none of the exclusion criteria).
- The intent-to-treat (ITT) population: ITT population consists of all subjects who took at least 1 dose of MITs or Abilify MyCite.
- Safety Sample: all subjects who wear any patch or take any tablet from the trial and have any safety assessment.

9.3 Handling of Missing Data for Primary and Secondary Endpoint Analysis

Missing data on PDA and/or detection latency measures will not be imputed.

9.4 **Statistical Analyses**

9.4.1 **Primary Endpoints**

The number of positive detections and PDA will be summarized for the D-Tect Patch for Cohort 1; the 95% CI of PDA will be provided using the Clopper-Pearson method. PDA is defined as PDA = $k \div n$, where n is the number of the total DOIs, and k is the number of positive detections by the patch.

For detection latency, summary statistics will be provided for Patch Detection Latency, Ingestion Data Transfer Latency, and Total Detection Latency. Kaplan-Meier curves will be plotted for all of the latency times.

9.4.2 Secondary Endpoint

The frequency and severity of AEs, device-related AEs, SAEs, AEs leading to discontinuation, and unanticipated adverse device effects will be summarized.

9.4.2.1 **Adverse Events**

All AEs will be coded by system organ class and Medical Dictionary for Regulatory Activities (MedDRA) preferred term. The incidence of the following events will be summarized:

- AEs
- AEs by severity •
- AEs potentially causally related to the investigational device
- AEs with an outcome of death •
- **SAEs** •
- AEs leading to discontinuation of the investigational device

9.4.2.2 **Clinical Laboratory Data**

Not applicable.

9.4.2.3 **Physical Examination and Vital Signs Data**

Baseline vital signs data will be provided in a listing.

9.4.2.4 **Electrocardiogram Data**

Not applicable.

Confidential - Proprietary Information

40

9.4.3 Other Analyses

9.4.3.1 Analysis of Demographic and Baseline Characteristics

Baseline demographic characteristics including age, race, ethnicity, sex at birth, gender, etc, will be summarized by cohort using descriptive statistics. Summary statistics will consist of mean, median, minimum, maximum, and standard deviation for continuous variables and tabulations of frequency distributions for categorical variables.

9.5 Interim Analysis

No interim analysis or adaptive design are applicable.

Confidential - Proprietary Information

10 Supporting Documentation and Operational Considerations

10.1 Appendix 1: Regulatory, Ethical, and Trial Oversight Considerations

10.1.1 Ethics and Responsibility

This trial must be conducted in compliance with the protocol, FDA regulations, applicable ICH (International Council for Harmonisation) GCP guidance, international ethical principles derived from the Declaration of Helsinki and Council for International Organizations of Medical Science (CIOMS) guidelines, and applicable local laws and regulations. Each trial site will seek approval/favorable opinion by an IRB according to regional requirements, and the investigator will provide that documentation to the sponsor. The IRB will evaluate the ethical, scientific, and medical appropriateness of the trial. Further, in preparing and handling the eCRF and any safety information, the investigator, subinvestigator, and their staff will take measures to ensure adequate care in protecting subject privacy. To this end, a subject ID will be used to identify each subject.

Financial aspects, subject insurance, and the publication policy for the trial will be documented in the agreement between the sponsor and the investigator.

10.1.2 Informed Consent

Informed consent will be freely obtained from all subjects (or their guardian or legally acceptable representative, as applicable for local laws). The ICF will be approved by the same IRB that approves this protocol.

Each ICF will comply with the ICH GCP Guidelines and local regulatory requirements. The investigator will ensure that the sponsor reviews and authorizes any written site-specific ICF used in the trial before submission to the IRB.

Investigators may discuss trial availability and the possibility for entry with a potential subject without first obtaining consent. However, informed consent must be obtained and documented before initiation of any procedures that are performed solely for the purpose of determining eligibility for this trial, including withdrawal from current medication(s).

Potential subjects are free to refuse entry into the trial, or withdraw from the trial at any time, without justification, and there will be no consequences to their further care.

Once appropriate essential information has been provided and fully explained in layman's language to the subject by the investigator (or a qualified designee), and it has been documented that the subject has had the opportunity to ask questions and have those questions answered, the IRB-approved paper ICF will be signed and dated by both the

Confidential - Proprietary Information

42

subject and the person obtaining consent (investigator or designee), as well as by any other parties required by the IRB. The subject will receive a copy of the signed ICF; the original shall be kept on file by the investigator.

Subjects may be asked to sign additional ICFs if the protocol is amended and the changes to the protocol result in additional information that needs to be provided to the subjects, so that they can make a knowledgeable and voluntary decision on continued trial participation. Female partners of male subjects who become pregnant during the course of the trial may be asked to sign additional ICFs in order to collect additional information regarding the nonsubject partner and fetus.

